2.4.2 Prior, concomitant and post therapies

Prior anti-cancer therapy

The number and percentage of subjects who received any prior anti-neoplastic medications, prior anti-neoplastic radiotherapy or prior anti-neoplastic surgery (excluding biopsy procedures) will be summarized by treatment arm. Prior anti-neoplastic medications will be summarized by therapy type (e.g. chemotherapy, hormonal therapy, etc.), setting (e.g. adjuvant, metastatic, etc.) and also by lowest ATC class, preferred term and treatment. Summaries will include total number of regimens, best response and time from last treatment to progression for the last therapy. The medication therapy type of any combination therapy will be classified based on the following order: immunotherapy, chemotherapy, biologic therapy (other than immunotherapy), targeted therapy, hormonal therapy. For example, a combination therapy of chemotherapy and biologic therapy will be classified as ‘chemotherapy’. For radiotherapy, time since last radiotherapy, locations and setting of last therapy will be summarized. For prior surgery, time since last surgery, procedure and residual disease of last therapy will be summarized.

Separate listings will be produced for prior anti-neoplastic medications, radiotherapy, and surgery.

Anti-neoplastic medications will be coded using the World Health Organization (WHO) Drug Dictionary (WHO-DD); Details regarding MedDRA and WHO-DD version will be included in the footnote in the tables/listings.

The above analyses will be performed using the FAS.

Post treatment anti-cancer therapy

Anti-neoplastic therapies since discontinuation of study treatment will be listed and medications will be summarized by ATC class, preferred term, overall and by treatment group by means of frequency counts and percentages using FAS.

Concomitant medications

Concomitant therapy is defined as all interventions (therapeutic treatments and procedures) other than the study treatment administered to a subject coinciding with the study treatment period. Concomitant therapy include medications (other than study drugs) starting on or after the start date of study treatment or medications starting prior to the start date of study treatment and continuing after the start date of study treatment.

Concomitant medications will be coded using the WHO Drug Reference Listing (DRL) dictionary that employs the WHO Anatomical Therapeutic Chemical (ATC) classification system and summarized by lowest ATC class and preferred term using frequency counts and percentages. Concomitant non-drug therapies/procedures will be coded using MedDRA and summarized by SOC and preferred term. Concomitant medications with immunosuppressive intent (agents to treat suspected irAEs) will be summarized by lowest ATC class and preferred term using frequency counts and percentages. Concomitant medications with immunosuppressive intent will be programmatically flagged using a pre-specified list from the clinical team.

All concomitant systemic corticosteroids will be summarized by lowest ATC class and preferred term using frequency counts and percentages. Additionally, the cumulative number of days while on study treatment that a subject took any systemic corticosteroid will be summarized. Systemic corticosteroids) will be programmatically flagged using a pre-specified list from the clinical team.

All summaries will include:

1. Medications starting on or after the start of study treatment but no later than 30 days after last dose of study treatment and
2. Medications starting prior to start of study treatment and continuing after the start of study treatment.

Additional summaries will be provided to report medications starting between 31 days after last dose of study treatment and up to 150 days after last administration of LAG525/spartalizumab.

All reported concomitant therapies will be listed. Any concomitant therapies starting more than 150 days after the last dose of LAG525 or spartalizumab, or 30 days after last dose of study treatment whichever comes last, will be flagged in the listing. The safety set will be used for all concomitant medication tables and listings.

2.5 Analysis of the primary objective

The primary objective is to assess the antitumor activity of the three treatment arms LAG525 + spartalizumab, LAG525 + spartalizumab + carboplatin and LAG525 + carboplatin, in subjects with advanced TNBC in first or second line of therapy, as measured by the objective response rate (ORR) per investigator's assessment according to RECIST v1.1.

2.5.1 Primary endpoint

The primary endpoint of the study is ORR defined as the proportion of subjects with best overall response (BOR) of complete response (CR) or partial response (PR) according to RECIST 1.1 (see [Appendix 3 of the study protocol](#)). ORR will be calculated based on the FAS using local investigators review of tumor assessment data. Tumor assessments performed before the start of any further antineoplastic therapy (i.e. any additional secondary antineoplastic therapy or surgery) will be considered in the assessment of BOR. Treatment with bisphosphonates or denosumab for pre-existing painful bone metastases and limited-field palliative radiotherapy is permitted as per protocol, and will not be considered as new antineoplastic therapy.

BOR is defined as the best response recorded from the randomization date until disease progression as per RECIST 1.1. Complete and partial responses must be confirmed by repeat assessments that should be performed not less than 4 weeks after the criteria for response are first met.

The BOR for each subject is determined from the sequence of overall (lesion) responses according to the following rules:

CR = at least two determinations of CR at least 4 weeks apart before progression

PR = at least two determinations of PR or better at least 4 weeks apart before progression (and not qualifying for a CR)

SD = at least one SD assessment (or better) > 5 weeks after randomization (and not qualifying for CR or PR).

PD = progression \leq 13 weeks after randomization (and not qualifying for CR, PR or SD).

UNK = all other cases (i.e., not qualifying for confirmed CR or PR and without SD after more than 5 weeks or early progression within the first 13 weeks)

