6.2 Other treatment(s)

6.2.1 Concomitant therapy

In general, concomitant medications and therapies deemed necessary for the supportive care (e.g. such as anti-emetics, anti-diarrhea) and safety of the participant are allowed as follows:

- Medications to prevent or treat nausea or vomiting.
- Anti-diarrheal medications (e.g., loperamide) for participants who develop diarrhea.
- Pain medication to allow the participant to be as comfortable as possible.
- Treatment with bisphosphonates or denosumab and/or limited-field palliative radiotherapy or surgery for pre-existing painful bone metastases is permitted. Participants requiring initiation of such treatment during the course of the study must be evaluated for disease progression. Radiotherapy like any concomitant medication must be listed on the CRF. LAG525/spartalizumab should be held for ≥1 week prior to radiotherapy or surgery, and may be resumed ≥2 weeks after radiation or surgery, provided the participant has recovered from radiation or surgery related toxicity. Caution is advised for radiation to fields that include lung tissue because of the potential increased risk of pneumonitis when lung radiotherapy is used during therapy with checkpoint inhibitors.
- Immunosuppressive agents to treat suspected irAEs.
- Hematopoietic colony-stimulating growth factors (e.g. G-CSF, GM-CSF, M-CSF), thrombopoietin mimetics or erythroid stimulating agents as per local or published guidelines; in case of anemia, thrombocytopenia or neutropenia, potential immunemediated etiology should be ruled out.
- Nutritional support or appetite stimulants.
- Oxygen therapy and blood products or transfusions.

• Inactivated vaccines.

The participant must be told to notify the investigational site about any new medications he/she takes after the start of the study drug. All medications, procedures and significant non-drug therapies (including physical therapy, herbal/natural medications, and blood transfusions) administered after the participant was enrolled into the study must be recorded in the concomitant medications / significant non-drug therapies or procedures pages.

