6.2.1.1 Permitted concomitant therapy requiring caution and/or action

Anticoagulation and anti-aggregation agents are permitted if the participants are already at stable doses for > 2 weeks at time of first dose and International Normalized Ratio (INR) should be monitored as clinically indicated per investigator's discretion. However, ongoing anticoagulant therapy should be temporarily discontinued to allow tumor sample according to the institutional guidelines.

In cases of isolated brain progression or other local progression, participants may receive palliative radiotherapy or surgery. In addition, localized, palliative radiotherapy for preexisting bone/liver metastases is permitted. LAG525/spartalizumab should be held for ≥1 week prior to radiotherapy or surgery. LAG525/spartalizumab may be resumed ≥2 weeks after radiation or surgery, provided the participant has recovered from radiation or surgery related toxicity. Chemotherapy should be held based on institutional guidelines. If palliative radiotherapy or surgery is initiated after start of study treatment, the reason for its use must be clearly documented and progression as per RECIST 1.1 must be assessed and documented. In case of continuation of study treatment beyond disease progression by RECIST 1.1, the participant will continue assessments as defined in Section 8.

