If a participant is known to have a contraindication to CT intravenous (IV) contrast media or develops a contraindication during the trial, a non-contrast CT of the chest (MRI is not recommended due to respiratory artifacts, however if CT is not feasible per local regulations, MRI can be performed instead) plus a contrast-enhanced MRI (if possible) of the abdomen and pelvis should be performed.

A whole body bone scan should be performed per institutional standard of care (e.g., Tc-99 bone scan, whole body bone MRI, Fluorodeoxyglucose positron emission tomography (FDG-PET) or sodium fluoride (NaF) PET). Localized CT, MRI or X-rays should be acquired for all skeletal lesions identified on the screening whole body bone scan, which are not visible on the chest, abdomen and pelvis CT/MRI.

If clinically indicated, CT or MRI of other areas (e.g., neck) of disease as appropriate should be performed.

Any potentially measurable lesion that has been previously treated with radiotherapy should be considered as a non-measurable lesion. However, if a lesion previously treated with radiotherapy has clearly progressed since the radiotherapy, it can be considered as a measurable lesion.

Chest x-rays and ultrasound should not be used to measure tumor lesions.

Post-baseline imaging assessments

Imaging assessments as described in Table 8-2 should be performed using the same imaging modality used at baseline, irrespective of study treatment interruption or actual dosing (see Table 8-1). Imaging assessments for response evaluation will be performed every 6 weeks (+/- 7 days) during the first 9 months, and every 12 weeks (+/- 7 days) thereafter as outlined below. Imaging assessments should be scheduled using the randomization date as the reference

date (not the date of the previous tumor assessment), and should be respected regardless of whether treatment with study treatment is temporarily withheld or unscheduled assessments performed.

Additional imaging assessments may be performed at any time during the study at the investigator's discretion to support the efficacy evaluations for a participant, as necessary. Clinical suspicion of disease progression at any time requires a physical examination and imaging assessments to be performed promptly rather than waiting for the next scheduled imaging assessment.

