Example: In a case where confirmation of response is required the sum of lesion diameters is 200 mm at baseline and then 140 mm - 150 mm - 140 mm - 160 mm - 160 mm at the subsequent visits. Assuming that non-target lesions did not progress, the overall lesion response would be PR - SD - PR - PR - PR. The second assessment with 140 mm confirms the PR for this patient. All subsequent assessments are considered PR even if tumor measurements decrease only by 20% compared to baseline (200 mm to 160 mm) at the following assessments.

If the patient progressed but continues study treatment, further assessments are not considered for the determination of best overall response.

Note: these cases may be described as a separate finding in the CSR but not included in the overall response or disease control rates.

The best overall response for a patient is always calculated, based on the sequence of overall lesion responses. However, the overall lesion response at a given assessment may be provided from different sources:

- Investigator overall lesion response
- Central Blinded Review overall lesion response
- Novartis calculated overall lesion response (based on measurements from either Investigator or Central Review)

The primary analysis of the best overall response will be based on the sequence of investigator/central blinded review/calculated (investigator)/calculated (central) overall lesion responses.

Based on the patients' best overall response during the study, the following rates are then calculated:

Overall response rate (ORR) is the proportion of patients with a best overall response of CR or PR. This is also referred to as 'Objective response rate' in some protocols or publications.

Disease control rate (DCR) is the proportion of patients with a best overall response of CR or PR or SD. The objective of this endpoint is to summarize patients with signs of "activity" defined as either shrinkage of tumor (regardless of duration) or slowing down of tumor growth.

Clinical benefit rate (CBR) is the proportion of patients with a best overall response of CR or PR, or an overall lesion response of SD or Non-CR/Non-PD which lasts for a minimum time duration (with a default of at least 24 weeks in breast cancer studies). This endpoint measures signs of activity taking into account duration of disease stabilization.

Another approach is to summarize the progression rate at a certain time point after baseline. In this case, the following definition is used:

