Situation F: New cancer therapy given: the handling of this situation must be specified in detail in the protocol. However, option (1) (ITT) is the recommended approach; events documented after the initiation of new cancer therapy will be considered for the primary analysis i.e. progressions and deaths documented after the initiation of new cancer therapy would be included as events. This will require continued follow-up for progression after the start of the new cancer therapy. In such cases, it is recommended that an additional sensitivity analysis be performed by censoring at last adequate assessment prior to initiation of new cancer therapy.

Option (2), i.e. censoring at last adequate assessment may be used as a sensitivity analysis. If a high censoring rate due to start of new cancer therapy is expected, a window of approximately 8 weeks performed after the start of new cancer therapy can be used to calculate the date of the event or censoring. This should be clearly specified in the analysis plan.

In some specific settings, local treatments (e.g. radiation/surgery) may not be considered as cancer therapies for assessment of event/censoring in PFS/TTP/DoR analysis. For example, palliative radiotherapy given in the trial for analgesic purposes or for lytic lesions at risk of fracture will not be considered as cancer therapy for the assessment of BOR and PFS analyses. The protocol should clearly state the local treatments which are not considered as antineoplastic therapies in the PFS/TTP/DoR analysis.

The protocol should state that tumor assessments will be performed every x weeks until radiological progression irrespective of initiation of new antineoplastic therapy. It is strongly recommended that a tumor assessment is performed before the patient is switched to a new cancer therapy.

Additional suggestions for sensitivity analyses

Other suggestions for additional sensitivity analyses may include analyses to check for potential bias in follow-up schedules for tumor assessments, e.g. by assigning the dates for censoring and events only at scheduled visit dates. The latter could be handled by replacing in Table 16-6 the "Date of last adequate assessment" by the "Date of previous scheduled assessment (from baseline)", with the following definition:

• Date of previous scheduled assessment (from baseline) is the date when a tumor assessment would have taken place, if the protocol assessment scheme was strictly

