2.5.3 Handling of missing values/censoring/discontinuations

Subjects with unknown or missing BOR as per RECIST 1.1 will be counted as failures. If there is no baseline tumor assessment, all post-baseline overall lesion responses are expected to be ‘Unknown’. If no valid post-baseline tumor assessments are available, the best overall response must be “Unknown” unless progression is reported. If a complete response is not confirmed, the best overall response must be “Unknown” unless it occurs after the first 5 weeks (stable disease), or confirmed partial response or progression is reported. If a partial response is not confirmed, the best overall response must be “Unknown” unless it occurs after the first 5 weeks (stable disease) or progression is reported. For the computation of ORR, these subjects with unknown BOR will be included in the FAS and will be counted as ‘failures’.

Only tumor assessments performed on or before the start of a new antineoplastic treatment other than study drug(s) (not considering palliative radiotherapy) will be considered in the assessment of BOR.

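### Palliative radiotherapy never closes best overall response and no rule removes a target lesion irradiated on study, so radiation shrinkage can score as a drug response in ORR

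*SAP*

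**What the plan says.** **Radiotherapy and BOR.** SAP 2.5.1 ends BOR collection at any further antineoplastic therapy, including surgery, but adds that "limited-field palliative radiotherapy is permitted as per protocol, and will not be considered as new antineoplastic therapy". SAP 2.5.3 repeats the cut-off in wider terms: "Only tumor assessments performed on or before the start of a new antineoplastic treatment other than study drug(s) (not considering palliative radiotherapy"). Neither section limits the exemption by site or by whether the irradiated lesion is a target lesion.

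**What is permitted.** Protocol 6.2.1.1 says that "localized, palliative radiotherapy for preexisting bone/liver metastases is permitted". If radiotherapy starts after study treatment, "progression as per RECIST 1.1 must be assessed and documented". Protocol 6.2.1 says: "Radiotherapy like any concomitant medication must be listed on the CRF".

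**Lesions irradiated before baseline.** Protocol 8.3.1 says: "Any potentially measurable lesion that has been previously treated with radiotherapy should be considered as a non-measurable lesion", unless it has clearly progressed since. There is no counterpart for lesions irradiated on study.

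**Response derivation.** Protocol 16.3.2.3 requires every baseline target lesion to be followed and keeps its diameter in the sum. Table 16-2 defines PR as a fall of at least 30% in that sum. It assigns UNK only when a target lesion was not assessed or was assessed by another method. SAP 2.5.1 requires confirmation at least 4 weeks later. Protocol 16.3.3.1 closes BOR at progression: "If the patient progressed but continues study treatment, further assessments are not considered for the determination of best overall response".

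**Exempt local treatments.** Appendix 3 (Protocol 16.3.3.2.10) gives as an example of an exempt treatment "palliative radiotherapy given in the trial for analgesic purposes or for lytic lesions at risk of fracture", and asks the protocol to state clearly which local treatments are exempt. Protocol 12.4.3 applies the antineoplastic cut-off for BOR with no radiotherapy exemption.

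**The concern.** ORR is meant to measure the activity of the study drugs. A liver metastasis is often measurable soft tissue, and target lesions are chosen largely by size, so a permitted radiotherapy field can contain a target lesion. Once that happens, local treatment may reduce a diameter that still counts in the sum. The protocol guards against this for earlier radiotherapy, by calling the lesion non-measurable, but not for radiotherapy given after randomization.

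The error can only add responders. Assessment is open-label and by the investigator, central review is optional (Protocol 8.3.1), and the one ORR sensitivity analysis in SAP 2.5.4 concerns unconfirmed responses. Nothing planned would show how many responses depended on radiotherapy.

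**Working it through.** **1. The plan's own figures.** Inputs: prior Beta(0.35/0.65, 1) = Beta(0.5385, 1); posterior Beta(0.5385 + y, 1 + n − y); PPE if the posterior mean is at least 0.35 and Pr(ORR ≥ 25%) is at least 0.90 (Protocol Appendix 2, SAP 5.4.1).

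| n | Responders | Posterior mean | Pr(ORR ≥ 25%) | PPE |
|---|---|---|---|---|
| 32 | 11 | 11.5385/33.5385 = 0.344 | 0.878 | no |
| 32 | 12 | 12.5385/33.5385 = 0.374 | 0.939 | yes |
| 34 | 11 | 11.5385/35.5385 = 0.325 | 0.829 | no |
| 34 | 12 | 12.5385/35.5385 = 0.353 | 0.906 | yes |

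The threshold of 12 at n=32 and the 0.939 agree with SAP 5.4.1. Exact P(Bin(32, p) ≥ 12) at p = 25, 30, 35, 40 and 45% is 0.080, 0.228, 0.449, 0.677 and 0.849. Protocol Table 12-2 gives 0.079, 0.228, 0.448, 0.675 and 0.847. All differ by less than 0.002, which fits a simulation. The operating characteristics are sound; the issue is what counts as a response.

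The n=34 rows are included because Amendment 4 reports 34 randomized in each of Arms 2 and 3.

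**2. Tracing the route.** For radiation shrinkage to score as a response, all of these must hold:
- a target lesion lies in a permitted palliative field;
- the progression assessment at the start of radiotherapy does not show RECIST PD, otherwise BOR closes;
- the whole target sum falls by at least 30% from baseline, with no new lesion and no progression elsewhere;
- the fall is confirmed at least 4 weeks later.

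If the irradiated lesion is a share w of the baseline sum and the other target lesions do not change, it must shrink by 0.30/w. So w must be at least 0.30, and a lesion making up half the sum must shrink by 0.30/0.50 = 60%. If the other target lesions shrink too, less is needed. Nothing in the SAP or Appendix 3 stops the sequence once these conditions are met.

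**3. Size.** One extra responder adds 1/34 = 2.9 to 1/32 = 3.1 percentage points to an arm's observed ORR. The documents do not say how many participants were irradiated, so the rate of false response is an assumption. With true ORR 25% and 1, 2 or 3 points added, P(at least 12 responders) is:

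| Points added | n=32 | n=34 |
|---|---|---|
| 0 | 0.080 | 0.119 |
| 1 | 0.103 | 0.149 |
| 2 | 0.129 | 0.183 |
| 3 | 0.158 | 0.221 |

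Three points is about one participant per arm (0.03 × 32 = 0.96). If exactly one response in an arm were due to radiotherapy, 11 drug responders would suffice; at true ORR 25% that has probability 0.154 at n=32 and 0.211 at n=34.

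**The case against.** The strongest reply is that the route is narrow and already guarded. Progression must be assessed when radiotherapy starts, and PD closes BOR, so radiotherapy given for growth that meets RECIST PD cannot yield a response. Many bone lesions are non-measurable and never enter the sum. PR needs a large, confirmed fall in the whole sum. This stands and limits the size of the problem. It leaves open the case of a preexisting, non-progressing liver target lesion.

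A second reply is that the primary analysis is over. Amendment 4 reports that no arm met PPE at the 27-Feb-2020 cut-off, and SAP section 1 describes the latest SAP amendment as serving a safety and PK close-out report without inferential analysis. A new primary rule now would be post hoc. This also stands, and it favors a sensitivity analysis over re-deriving the primary result.

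Three stronger readings are tempting but not supported:
- *That Appendix 3 confines the exemption to pain or fracture risk.* It offers those uses as an example and leaves the list to the protocol.
- *That PFS and DOR are affected in the same way.* The exemption is written in the BOR sections. SAP 2.7.3 censors at new anticancer therapy and does not mention radiotherapy, so carrying the exemption over is inference.
- *That surgery is a similar gap.* SAP 2.5.1 already counts it as therapy that ends BOR.

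**Conclusion.** The concern holds for BOR and ORR. As written, the SAP can credit the study drugs with shrinkage produced by on-study radiotherapy to a target lesion. The bias is one-directional and reaches an endpoint where moving from 11 to 12 responders changes the decision at n=32 and at n=34.

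Its size is unknown. The rise from 0.080 to between 0.103 and 0.158 at n=32 rests on an assumed 1 to 3 points of false response at true ORR 25%. A reader might infer that reported responses were in fact inflated, or that a wrong decision was made. The documents show neither: no count of irradiated participants is given, and no arm met PPE. What remains at stake is the reported ORR and any reuse of this wording in a later trial.

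**What to change.** **Rule, for BOR and ORR only.** In SAP 2.5.1 and 2.5.3, state that a target lesion irradiated after randomization is non-evaluable for response from that date, so the overall response for BOR is UNK unless PD. Keep the exemption for radiotherapy to non-target lesions. Responses confirmed before radiotherapy are untouched.

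**Minimum, since the primary analysis is complete.** Report an ORR sensitivity analysis that counts as non-responders those participants whose response was first met or confirmed after target-lesion radiotherapy, and give their number by arm.

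**Leave SAP 2.7.3 alone.** It treats an UNK assessment as missing and censors an event that follows two or more missing assessments. The UNK rule there could censor true progressions or deaths. No surgery clause is needed.

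**Reconcile the texts.** SAP 2.5.1 and 2.5.3 should agree with Protocol 12.4.3, which has no radiotherapy exemption, and the protocol should name the exempt local treatments as Appendix 3 asks. SAP section 4 lists no change to protocol-specified analyses, although the exemption is one. This concerns the analysis only; no clinical rule on radiotherapy need change.

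**Cost.** A few lines of SAP text and a match of radiotherapy site to the target-lesion list. Radiotherapy is listed on the CRF, but the documents do not say whether the irradiated site is recorded in enough detail to match. A few assessments become UNK, and a genuine responder not yet confirmed before radiotherapy may count as a failure.
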